This is a randomized, controlled, single-blinded, pilot trial to study the feasibility, safety, and efficacy of acupuncture in IC/PBS women. Women will be recruited from the patient population of the Loyola University Medical Center who meet criteria for diagnosis of IC/PBS. This trial had 2 arms comparing the treatment of IC/PBS symptoms with acupuncture or sham/minimal acupuncture (placebo). Thirty (30) patients with IC/PBS will be enrolled as study participants into the study. Fifteen (15) will be allocated in the treatment classical acupuncture + medical management of IC and fifteen (15) will be allocated in the control sham/minimal acupuncture + standard medical treatments of IC. The acupuncturist will interview each patient and perform an exam. A standardized acupuncture treatment will be assigned, and both groups will receive 7 acupuncture treatments that follow a standardized protocol on classical acupuncture points, with or without mild electrical stimulation versus sham/minimal acupuncture. Acupuncture needles are single use, sterile and disposable. Standard acupuncture treatment protocol will include 4 gates plus GV 20 to reduce anxiety and help with relaxation and to assess acupuncture naïve patient's response to needles during their first acupuncture encounter. Subsequent visits would include administration of curious meridian Chong Mo paired with Yang Ming. 4 Hz low level electrical stimulation will be applied. Control group will receive sham/minimal acupuncture with low level electrical stimulation. The sham intervention (also described as minimal intervention) will use superficial needle insertion at body locations not recognized as true acupoints. Patients will be explained that various acupuncture treatment protocols will be tested including "minimal acupuncture", therefore, the control group will not be aware of receiving sham acupuncture. These described acupuncture treatments are well accepted treatment protocols for women with pelvic pain and bladder complaints.

Acupuncture or sham needle treatments will be performed once a week for 7 weeks. All subjects will be reassessed following the 7-week intervention phase and then 12 weeks from initiation of study. All subjects will be treated by single acupuncture practitioner ([name]) who is also a board certified urologist specializing in IC/PPS and is a current associate member of American Academy of Medical Acupuncture and board eligible for the American Board of Medical Acupuncture.

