Sequencing Approach. Bacterial DNA will be isolated from 0.5 ml of each urine sample, randomly fragmented, modified for and sequenced using Illumina's MiSeq technology. This technology allows for sequence of more than 200 nucleotides of DNA from each strand of the DNA duplex to be generated, facilitating the downstream bioinformatics analysis. WGS by MiSeq technology is expected to generate more than 100X coverage, the average number of sequences representing a given nucleotide from the generated sequence, for each sample. This magnitude of data allows for samples to be multiplexed, individually barcoded, and sequenced at once.

Bioinformatics Approach. Quality control & de-multiplexing, the separation of each individual sample from the group based upon their barcode, the sequence data can be readily achieved with MiSeq Reporter software from Life Technologies (current version: 2.0). Only high quality reads (\geq Q20) will be kept for analysis. Reads will be aligned and assembled using open source algorithms such as the AMOS and CABOG assembler packages to bioinformatically generate the genome of a specific bacterium.

Schedule of Measures:	Baseline	Post Acupuncture Completion	12 Weeks from Baseline	
Demographics	Х	Х	Х	
Questionnaires	Х	Х	Х	
Physical exam	Х	Х	Х	
Urine Specimen	Х	Х	Х	

Table 1. Schedule of measures for the proposed study.

F. DATA ANALYSIS/SAMPLE SIZE ESTIMATION:

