The primary objective is to compare the mean BPI-SF worst pain score at following acupuncture between groups. All other analyses are secondary outcomes. A separate linear mixed effects model will regress each pain score outcome on group (minimal versus electro-acupuncture), time (baseline, end of treatment, or end of follow-up), and a group by time interaction. Random intercepts will be included to account for within-patient correlation. Adjusted means and standard errors will be estimated, and main effects and the group by time interaction will be formally tested within the mixed model. A similar linear mixed effects model will regress relative abundance of uropathogen on group, time, and the group by time interaction. Based on the prior work of Crew KD et al.³⁷, a sample size of 30 participants (15 per arm) was calculated to yield 90% power to detect a reduction of 2.5 on the BPI-SF worst pain item at a 5% significance level, assuming a standard deviation of difference in score between treatment groups of 2.5 points. This includes a dropout rate of 10% A reduction of at least 2 points on the BPI-SF worst pain item is considered to be a clinically meaningful decrease based on the literature³⁸. All statistical analyses will be two-sided and performed using SAS 9.4 (SAS Institute, Cary, NC).

G. FUTURE DIRECTIONS: The impact and potential benefits of identifying new nonpharmacologic treatment in women with IC/PBS will be critical to reduce disease severity and improve quality of life across female IC/PBS and all CPP subtypes. These same methods will be employed for future clinical trials in IC/PBS and other CPP subtypes. In future studies, participants could be reassessed monthly for 6 months after post-intervention assessment (6 months after completing the treatment protocol), and subjects who relapse could receive one to two booster/maintenance acupuncture sessions with additional studies performed on the urinary microbiome.

H. TIMELINE:

Research Activity	Year 1 (2013 – 2014)			
	Qt 1	Qt 2	Qt 3	Qt 4
Recruitment and Evaluation of Participants	Х	Х	Х	
Data Collection	Х	Х	Х	
Data Analysis/Manuscript writing/editing			Х	Х

REFERENCES CITED:

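### Section F never names a test of the primary comparison: the listed tests answer other questions, and baseline is not used to sharpen the end-of-treatment contrast

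*Combined protocol and SAP*

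**What the plan says.** Section F (Data Analysis/Sample Size Estimation) states the aim: "The primary objective is to compare the mean BPI-SF worst pain score at following acupuncture between groups". It then adds: "All other analyses are secondary outcomes".

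The model for each pain score has group, "time (baseline, end of treatment, or end of follow-up), and a group by time interaction. Random intercepts will be included". Baseline is therefore one of three outcome visits, each arm has its own baseline mean, and no baseline covariate appears. For inference the section says "Adjusted means and standard errors will be estimated" and "main effects and the group by time interaction will be formally tested within the mixed model". It names no between-group contrast, no deciding test and no deciding visit, and no other section does so.

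Two visits come after treatment. The Acupuncture Component section says: "All subjects will be reassessed following the 7-week intervention phase and then 12 weeks from initiation of study". Table 1 has the columns Baseline, "Post Acupuncture Completion" and 12 Weeks from Baseline.

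**The concern.** The primary question concerns one difference at one time. The listed tests concern something else:

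- **Group main effect.** As usually computed (averaged over visits), it is the mean of three differences, and the baseline one has expectation zero. A real end-of-treatment effect is diluted.
- **Time main effect.** It describes change in both arms together and says nothing about efficacy.
- **Group-by-time interaction.** With three visits it has two degrees of freedom. It asks whether the arms differ in profile anywhere, so an effect confined to week 12 can make it significant.

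An analyst who follows the text could declare success or failure on a question the trial did not set as primary. With no deciding test named, the choice can also be made after the data are seen. Separately, baseline worst pain is collected but the model does not use it to sharpen the treatment comparison.

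**Working it through.** **Inputs.** From Section F: 15 per arm, effect 2.5 points, two-sided 5%, SD 2.5 ("assuming a standard deviation of difference in score between treatment groups of 2.5 points"), and three visits. The SD is read first as the per-arm SD of a score; other readings follow. The within-patient correlation ρ is not in the documents. I assume 0.5, with a range of 0.3 to 0.7, and equal SDs and complete data.

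**The plan's own figure.** Section F claims 90% power. A two-sample comparison with 15 per arm has noncentrality 2.5² / (2 × 2.5² / 15) = 7.5, which gives 75% (t) or 78% (normal). The 90% is not reproduced. That is a separate matter, and nothing below depends on it.

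**Formulas.** Let d be the true-minus-sham difference (in absolute size) at baseline, end of treatment and week 12, with mean d̄. Let σ be the per-arm SD and n the number per arm. At ρ = 0.5, σ = 2.5, n = 15:

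1. Group main effect: variance 2σ²(1+2ρ)/(3n) = 2 × 6.25 × 2/45 = 0.556, on 1 and 28 df.
   - Sustained (0, 2.5, 2.5): d̄ = 1.67, noncentrality 1.667²/0.556 = 5.0, power 58%.
   - End of treatment only (0, 2.5, 0): d̄ = 0.83, noncentrality 1.25, power 19%.
2. Interaction: noncentrality nΣ(d−d̄)²/(2σ²(1−ρ)), on 2 and 56 df.
   - Sustained, or week 12 only (0, 0, 2.5): Σ = 4.167, noncentrality 15 × 4.167/6.25 = 10.0, rejection 79%.
   - Half the effect left at week 12 (0, 2.5, 1.25): Σ = 3.125, noncentrality 7.5, power 66%.
3. Change from baseline to end of treatment: variance 4σ²(1−ρ)/n = 0.833, noncentrality 7.5 on 1 and 56 df, power 77%.
4. Direct end-of-treatment difference within the planned model: variance 2σ²/n = 0.833, noncentrality 7.5, Satterthwaite df 56, power 77%.
5. Baseline-adjusted end-of-treatment difference: variance 2σ²(1−ρ²)/n = 0.625, noncentrality 10.0 on 1 and 27 df, power 86%. Simulation gives 85%, since it also carries the cost of chance baseline imbalance.

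**Simulation.** Rejection rates from 40,000 trials per scenario (15 per arm, SD 2.5). The closed forms agree to about one point.

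| Test and scenario | ρ = 0.3 | ρ = 0.5 | ρ = 0.7 |
|---|---|---|---|
| Main effect, sustained | 67% | 58% | 51% |
| Main effect, end of treatment only | 23% | 19% | 17% |
| Interaction, sustained | 64% | 80% | 95% |
| Interaction, week 12 only | 64% | 80% | 95% |
| Adjusted contrast, week 12 only | 5% | 5% | 5% |
| Change contrast, sustained | 62% | 77% | 94% |
| Direct difference, sustained | 77% | 77% | 77% |
| Adjusted contrast, sustained | 78% | 85% | 95% |

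Under the null every test rejects in about 5% of trials. If either the main effect or the interaction could count as success, the two nearly independent tests give 1 − 0.95² = 9.75% (simulated 9.7%).

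**Variants at ρ = 0.5.**

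- 13 per arm, sustained: main effect 52%, interaction 73%, change 70%, direct 70%, adjusted 79%.
- 2.5 as the SD of the between-arm difference (per-arm 2.5/√2 = 1.77), 15 per arm, sustained: main effect 87%, interaction 98%, change 97%, direct 97%, adjusted 99%. The main effect still falls to 33% for an end-of-treatment-only effect, and the interaction still rejects in 98% for a week-12-only effect.
- 2.5 as the SD of change: σ² = 2.5²/(2(1−ρ)), which at ρ = 0.5 is again 6.25, so the results equal the main case.

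**Gain from baseline.** Relative variance of the adjusted contrast is 1−ρ² against the direct difference (0.91, 0.75, 0.51 at ρ = 0.3, 0.5, 0.7) and (1+ρ)/2 against change (0.65, 0.75, 0.85). It is below both throughout this range.

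**The case against.** The strongest reply is that the planned model already contains the right answer. Adjusted means by arm and visit are to be estimated, and their end-of-treatment difference follows from them. That is true, and it makes this a gap in specification and not an unusable model. But an estimable contrast is not a prespecified one, and the text plans no test of it.

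The visit is also less open than it may seem. The Acupuncture Component section uses the word following for the first reassessment and sets week 12 apart, so end of treatment is the natural reading. I adopt it, but one clear phrase should settle it.

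The harm cases are conditional. The main-effect figures matter only if that test decides, and they assume a test averaged over visits. Under reference coding the group coefficient would be the baseline difference, which is no better. A full effect at week 12 with none at end of treatment is a limiting case. With a sustained effect the interaction loses nothing against the change contrast (80% and 77%). With half the effect left at week 12 it has 66%, a moderate loss.

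Baseline adjustment is an efficiency gain and does not correct a bias. Its size depends on the unknown correlation: almost nothing over the direct difference at 0.3, little over change at 0.7, and negligible if the per-arm SD is 1.77.

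Finally, the Acupuncture Component section calls this a pilot. That lowers the stakes, but Specific Aim 2 is comparative efficacy and Section F claims power for it.

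**Conclusion.** The concern holds and should be corrected. Section F states one primary comparison and lists only tests that do not make it. This rests on the text alone. Its size rests on an assumed correlation of 0.3 to 0.7, equal SDs, complete data and the per-arm reading of the SD. On those terms:

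- the main effect targets 1.67 or 0.83 points instead of 2.5, with 51% to 67% power for a sustained effect and 17% to 23% for an end-of-treatment-only effect;
- the interaction would be significant in 64% to 95% of trials with no end-of-treatment effect and 2.5 points at week 12.

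The mismatch persists under the smaller SD, where the precision gain from adjustment nearly vanishes. The model itself is usable. What is missing is the deciding test and a stated use of baseline.

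**What to change.** In Section F, name one primary test: the baseline-adjusted true-minus-sham difference in BPI-SF worst pain at the post-completion visit, two-sided at 5%, reported with its 95% confidence interval. If the sponsor meant week 12, the text should say so instead. Either of two models gives the contrast:

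- (a) the two post-baseline visits as outcomes, with group, time, group-by-time, baseline worst pain and baseline-by-time; or
- (b) all three visits as outcomes, with the baseline mean constrained to be equal across arms.

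I suggest unstructured covariance with Kenward-Roger degrees of freedom, both available in SAS 9.4. This is a standard choice; the calculations above assume exchangeable correlation and do not show that it is needed. List the week-12 contrast, the main effects and the overall interaction as secondary.

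The cost is a few sentences in the plan and a few lines of SAS, with no new data and no extra visits.

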The reports that acupuncture's influence may be partially expressed through immune mechanisms are reinforced by the understanding that beta endorphin and met-enkephalin seem to be mediators between the central nervous system and immune system. The two substances have been shown to enhance natural killer cell activity and met-enkephalin increases in vitro T-lymphocyte rosette formation from human T-lymphocytes (Josef M. Helms. Acupuncture energetics **1995** | ISBN-10: **1572507063** | ISBN-13: **978-1572507067** | Edition: **1**st).

It seems logical to theorize that acupuncture treatment may lead to urinary microbiome change.

We propose that changes in bladder microbiota leading to this enhanced cytokine response may result in symptoms associated with IC/PBS and that acupuncture, by modulating cytokine response, in turn has effect on the urinary microbiome.

Our *long term goal* is to determine pelvic pain mechanisms that will inform clinically-relevant classification and evidence-based treatment of women with IC/PBS and CPP. *The short term goal* of this application is to determine the safety, tolerability and efficacy of acupuncture in women with IC/PBS as a neuromodulative treatment and to characterize the urinary microbiome before and after acupuncture treatment. Our approach will advance the understanding of the contribution and consequences of peripheral pelvic nociception in IC/PBS. Our *central hypothesis* is that women with IC/PBS will benefit from acupuncture compared with sham treatment and acupuncture will have an effect on the urinary microbiome.

This proposed work **impacts** public health with contributions of rigorous clinical and translational methods, suitable for future NIH clinical research networks, to evaluate and assess treatment outcomes in women with IC/PBS. It is likely that these methods will have impact beyond this group of affected patients, such as CPP related to irritable bowel syndrome, vulvodynia, pregnancy, and endometriosis.

B. INNOVATION: We believe that the proposed research is innovative, as current pharmacologic strategies for IC/PBS have limited success and/or problematic side effects, yet acupuncture has not been studied in this population to date despite its proven efficacy in other chronic pain disorders¹¹. In addition, no study to date has correlated the urinary microbiome in IC/PBS with clinical characteristics or with response to acupuncture treatment.

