D. DESIGN OVERVIEW: This prospective randomized single blinded study will compare the effect of true acupuncture compared with sham/minimal acupuncture in women with IC/PBS (n=30). Symptomatic IC/PBS participants will not be asked to stop taking standing medications such as neurological agents in order to participate in the study. All current medications will be recorded and will measured using the Medication Quantification Scale (MQS III)^{23,24}. They will be asked to refrain from use of short-acting opioids/acetaminophen/non-steroid anti-inflammatory medications during study visits. IC/PBS participants will engage in 7 acupuncture sessions once weekly. Initial visit would assess participant's response to needle insertion. Standard classical/true acupuncture treatment will be administered during 6 following visits to treatment group (n=15) and sham/minimal acupuncture will be administered to control group. Menstrual cycle time points will be recorded for each visit. Clean catch voided urine samples and vaginal swab will be obtained prior to initiation of intervention, on completion of intervention and 12 weeks post onset of study visits.

E. RESEARCH STRATEGY:

Specific Aim 1: To determine the safety and tolerability of acupuncture in women with IC/PBS.

Hypothesis 1: Acupuncture treatment (true and sham) will be safe and tolerable in women with IC/PBS.

Specific Aim 2: To determine if acupuncture is effective in reducing pain in women with IC/PBS compared to sham treatment.

Hypothesis 2: True acupuncture treatment will be effective in the treatment of pain in women with IC/PBS compared with sham/minimal treatment.

Specific Aim 3: To determine the association between acupuncture responders and the urinary microbiome.

Hypothesis 2: Acupuncture responders will exhibit change in the urinary microbiome compared with nonresponders after acupuncture treatment.

STUDY DESIGN/METHODS:

Acupuncture Component:

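### Aim 3 compares responders with nonresponders, but the only microbiome model compares randomised arms, and responder is never defined

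*Combined protocol and SAP*

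**What the plan says.** Section E states Specific Aim 3 as "To determine the association between acupuncture responders and the urinary microbiome". Its hypothesis is: "Acupuncture responders will exhibit change in the urinary microbiome compared with nonresponders after acupuncture treatment". Section B presents this link as part of the study's novelty: "no study to date has correlated the urinary microbiome in IC/PBS with clinical characteristics or with response to acupuncture treatment".

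Section F gives one microbiome analysis: "A similar linear mixed effects model will regress relative abundance of uropathogen on group, time, and the group by time interaction". It is described as similar to the pain model, in which the term is "group (minimal versus electro-acupuncture", that is, the randomised arm. All analyses other than BPI-SF worst pain are secondary.

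Two items could serve as a response criterion, and neither is named as one. Section F says: "A reduction of at least 2 points on the BPI-SF worst pain item is considered to be a clinically meaningful decrease". The Clinical Measurements list includes the Patient Global Response Assessment (GRA), with no cut-off.

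The closing paragraphs of section A also hold a separate microbiome hypothesis: "acupuncture will have an effect on the urinary microbiome".

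**The concern.** Responder status and randomised arm are different variables. Some women given true acupuncture will not improve, and some given sham will. A model with arm, time and arm by time estimates whether microbiome change differs by assigned treatment. Aim 3 asks whether it differs by clinical outcome. If the analyst follows section F exactly, one of the three specific aims ends without an estimate or a test.

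The missing definition adds to this. The measure, threshold, visit and arms that count are all open. With 30 women, several defensible definitions would probably classify some of them differently. If the choice is made after the sequencing results are known, a reader cannot tell a planned association from a selected one. That is a risk created by the gap. Nothing in the documents shows that such a choice has been or would be made.

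**Working it through.** **Step 1. Aim against analysis.**

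| Item | Aim 3 (section E) | Microbiome model (section F) |
|---|---|---|
| Comparison | responders vs nonresponders | minimal vs electro-acupuncture |
| Variable | response, observed after randomisation | arm, fixed by randomisation |
| Hypothesis addressed | Aim 3 hypothesis | central hypothesis in section A |

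The other microbiome comparison in the protocol, 20 control women against IC/PBS cases (section C), has no model in section F and does not use response status. It does not fill the gap.

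**Step 2. Is responder defined by implication?** There are four elements to settle.
- Measure and threshold: the 2-point BPI-SF fall is called clinically meaningful but is not called response. The GRA has no cut-off.
- Visit: the hypothesis says only that the change follows treatment, which fits either end of treatment or 12 weeks.
- Arms: Hypothesis 1 writes "Acupuncture treatment (true and sham) will be safe and tolerable in women with IC/PBS", which gives some support for counting both arms. Aim 2 and the central hypothesis set acupuncture against sham.

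None of the four is fixed.

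**Step 3. Can the arm contrast substitute?** Let *d* be the difference in microbiome change between responders and nonresponders, *a* any direct effect of arm, and *pT* and *pS* the response rates in the true and sham arms. Then

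arm contrast = *a* + *d* × (*pT* − *pS*).

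- *a* = 0, *d* = 1 SD, rates 50%/50%: 0 + 1 × 0 = 0. There is a strong responder association and no arm contrast.
- *a* = 0, *d* = 1 SD, rates 70%/30%: 1 × 0.40 = 0.40 SD, which is not *d*.
- *a* = 0.5 SD, *d* = 0: 0.5 SD. There is an arm contrast and no responder association within arms.

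The arm contrast therefore does not determine *d* in either direction.

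**Step 4. What could the missing analysis deliver?** The plan gives no power figure for Aim 3. Its one calculation (30 women, 10% dropout) is for the primary pain comparison; only the head count is used here. Ten percent dropout leaves 30 × 0.9 = 27.

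Assumptions, none from the documents: the response rates below; change from baseline to end of treatment distributed as N(0,1) + *d* × responder; least squares of change on responder and arm; two-sided 5%; 20,000 simulated trials per scenario; trials with no responder contrast counted as non-rejections.

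| Response true/sham (%) | Power, *d* = 1, n = 30 | *d* = 1, n = 27 | *d* = 0.5, n = 30 |
|---|---|---|---|
| 70/30 | 0.633 | 0.589 | 0.216 |
| 60/30 | 0.676 | 0.627 | 0.224 |
| 60/40 | 0.704 | 0.655 | 0.242 |
| 50/50 | 0.721 | 0.669 | 0.250 |
| 40/20 | 0.620 | 0.568 | 0.206 |
| 30/15 | 0.544 | 0.498 | 0.184 |
| 30/10 | 0.502 | 0.457 | 0.168 |
| 20/10 | 0.432 | 0.393 | 0.148 |
| 20/20 | 0.522 | 0.473 | 0.174 |

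With 27 women and *d* = 0.5 the range is 14-23%. In the true arm alone (15 women) it is 28-41% for 1 SD and 10-14% for 0.5 SD.

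An analytic cross-check uses an unadjusted two-sample t test with noncentrality *d* / √(1/n1 + 1/n2). A 15/15 split gives 1/√(2/15) = 2.74 and 75% power at *d* = 1. A 6/24 split gives 1/√(1/6 + 1/24) = 2.19 and 56%. For an assumed responder share of 20-70%, 80% power needs a difference of about 1.06-1.32 SD with 30 women and 1.12-1.44 SD with 27.

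The simulation uses a two-visit change score, not the three-visit mixed model. Relative abundance is also bounded. With assumed skewed abundance left untransformed, the 1-SD figure for 30 women was about 33-65%.

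**The case against.** The strongest opposing case concerns weight. The protocol calls this a pilot, Aim 3 is secondary, and 30 women can say little about it: at a 0.5-SD shift the added model would have at most 25% power. This stands as a limit on what the analysis can show, and it is why the analysis should be labelled exploratory. It does not supply the missing estimate, and a small sample makes fixing the definition in advance more important.

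It can also be said that the 2-point fall is an implied responder definition. A reader might infer that, but section F uses it only to describe a clinically meaningful decrease. Even if it were accepted, no model contains it. The GRA is a genuine alternative, and the choice belongs to the sponsor.

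Pooling the arms is likewise a choice. Hypothesis 1 is a statement about safety, so its wording is thin support, and pooling assumes one responder effect common to both arms.

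A reader might further infer that the planned arm contrast is nearly powerless and the responder test clearly superior. The documents do not support this. The two address different questions, and any such comparison depends on assuming that arm has no direct effect. Section A proposes that acupuncture itself, through cytokine response, acts on the microbiome. With an assumed direct effect of 0.5-1 SD on top of a 1-SD responder shift, arm-contrast power is about 22-92%. The case for the change rests on the mismatch of questions.

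Finally, Clinical Measurements names only baseline and 12 weeks, from which a reader might infer that end-of-treatment pain scores will not exist. The Acupuncture Component, Table 1 and section F all include that visit, so this is a wording conflict to align.

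**Conclusion.** The concern holds as a mismatch between a stated aim and its analysis. No planned analysis contains response status, responder is undefined, and the plan as written gives no estimate for Aim 3. These conclusions rest on the text alone and need no assumption. The change should be made, but it is not critical: a reader might infer that the trial's main conclusion is at risk, and it is not, because BPI-SF worst pain by arm does not depend on any of this.

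The size of what is lost can only be illustrated. Under the assumed response rates and normal change scores, the missing analysis would have about 43-72% power for a 1-SD responder shift with 30 women, 39-67% with 27, and 15-25% for 0.5 SD with 30. A null result would therefore not exclude a moderate association.

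**What to change.** Before sequencing results are examined, amend section F as follows.

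1. Keep the arm-by-time model as the randomised test of the section A hypothesis.
2. Add one exploratory Aim 3 model of the same abundance outcome on responder status, time and responder by time, adjusted for arm and arm by time, with the contrast read at end of treatment.
3. Fix one responder definition. A fall of at least 2 points in BPI-SF worst pain from baseline to end of treatment is the natural choice, because it is the primary outcome measure and the only threshold the plan states. The sponsor should weigh the GRA as the alternative; it would need a cut-off.
4. Fit the model in women with both a baseline and an end-of-treatment BPI-SF, and report how many are excluded.
5. Fit the true acupuncture arm alone, without arm terms, as a sensitivity analysis.
6. Align Clinical Measurements with the Acupuncture Component, Table 1 and section F on the end-of-treatment visit.
7. Report the result as a non-randomised, low-power association for one abundance measure, not for the microbiome as a whole.

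The cost is SAP wording, one model and one sensitivity fit. No new data are needed, since Table 1 already schedules questionnaires and urine at that visit. The downsides are that response is a post-randomisation variable, dichotomising loses information, pooling assumes a common responder effect across arms, and power is limited, most of all in the true arm alone or if few women respond.
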